14.6. Secondary Analysis

CLUE Handling and Comfort Scores

CLUE Handling and Comfort scores after 1-week of lens wear will be analyzed separately using a linear mixed model adjusting for baseline scores as a covariate. Sequence of lens wear, lens type and period will be included in the model as fixed effects. Subject characteristics such as, gender, age and/or cylinder power made be included in the model if appropriate. Site ID will be included in the model as a random effect (G-side). The residual error between measurements within the same subject will be modeled using an unstructured (UN) covariance structure. If the model fails to converge with a UN covariance, then a compound systemic (CS) covariance structure will be used. The Kenward and Roger Method will be used for the denominator degrees of freedom.¹¹ CLUE Handling and Comfort scores for each study lens will be estimated using 97.5% confidence intervals (CI) constructed for the least-square means (LSM).

Secondary Hypothesis 1:

The null and alternative hypothesis to test for superiority of CLUE Handling score for the test lens relative to the threshold 61 are as follows:

$$\begin{aligned} H_0: \mu_{TTTTTTTT} &\leq 61 \\ H_A: \mu_{TTTTTTTT} &> 61 \end{aligned}$$

Where $\mu_{TTTTTTTT}$, represents the population mean for test lens after 1 week of lens wear with respect to CLUE Handling scores. Superiority will be declared if the lower limit of the 97.5% CI is above 61.

Secondary Hypothesis 2:

The null and alternative hypothesis to test for superiority of CLUE Comfort score for the test lens relative to the threshold 58 are as follows:

$$\begin{aligned} H_0: \mu_{TTTTTTTT} &\leq 58 \\ H_A: \mu_{TTTTTTTT} &> 58 \end{aligned}$$

Where $\mu_{TTTTTTTT}$, represents the population mean for test lens after 1 week of lens wear with respect to CLUE comfort scores. Superiority will be declared if the lower limit of the 97.5% CI is above 58.

14.7. Exploratory Analysis

Ability to see comfortably while driving during the day or Reduction in the feeling of tired eyes from using a computer or other digital device

Subjective responses for exploratory endpoints will be the outcome (*aval*) defined as category one if a subject's response is 'Excellent', 'Very Good', 'Fair', or 'Poor'.

My vision was clear enough to allow me to drive at night

Subjective responses for exploratory endpoints will be the outcome (*aval*) defined as category one if a subject's response is 'Strongly Agree' or 'Agree', the outcome is defined as category two if a subject's response is 'Not Applicable', 'Strongly Disagree', 'Disagree', or 'Neither Agree nor Disagree'.

Clinical Study Protocol
Johnson & Johnson Vision Care, Inc.

Statistical Model:

The outcome for each item will be analyzed separately using a generalized linear mixed model with a binary distribution and the logit as the link function. In each model, sequence of lens wear, period, lens type will be included as fixed effects. Site will be included as a random effect. Residual errors between measurements within the same subject will be modeled using an unstructured covariance (UN) structure. Comparisons between the test and control will be carried out using 2-sided 95% confidence intervals (CIs) constructed for the odds ratio (test over control). Non-inferiority will be concluded if a lower limit of a 95% CI is above 0.67.

Hypothesis Testing

The null and alternative hypothesis to test for non-inferiority of the test lens compared to the control lens will be conducted separately for each item as follows:

$$\begin{aligned} H_0: & \text{ OR} \leq 0.67 \\ H_a: & \text{ OR} > 0.67 \end{aligned}$$

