2.3. Hypotheses

Co-Primary Safety Hypotheses:

1. The percentage of eyes with one or more clinically significant, study-lens related, slit-lamp findings (Grade 3 or 4) following wear of the test lenses will be less than 5%.
2. At least 80% of lens fits will be acceptable at the dispensing visit.

Both co-primary *safety* hypotheses must be met in order to test any co-primary *efficacy* hypotheses.

Co-Primary Efficacy Hypotheses:

1. After approximately 1-week of wear, the mean monocular, high-luminance, high-contrast distance visual acuity for the test lens will be lower than 0.00 logMAR (equivalent to 20/20 Snellen visual acuity).
2. Following lens settling (at least 15 minutes) at the dispensing visit, at least 80% of lens fits will have absolute rotation less than or equal to 10 degrees.
3. Following lens settling (at least 15 minutes) at the dispensing visit, at least 80% of lens fits will have lens rotational stability with blink less than or equal to 5 degrees.
4. After approximately 1 week of wear, the mean overall CLUE™ Vision score for the test lens will be statistically greater than 62 points.

All safety and efficacy co-primary hypotheses must be satisfied in order to meet the study objectives and to test any secondary hypotheses.

Secondary Hypotheses:

1. After approximately 1 week of wear, the mean overall CLUE™ Handling score for the test lens will be greater than 61 points with 95% statistical confidence.
2. After approximately 1 week of wear, the mean overall CLUE™ Comfort score for the test lens will be greater than 58 points with 95% statistical confidence.

Clinical Study Protocol
Johnson & Johnson Vision Care, Inc.

Exploratory Hypotheses:

1. After approximately 1 week of wear, the test lens will be non-inferior to the control lens with respect to at least one of the following subjective questionnaire items asked at the follow-up visit:
 - a. Ability to see comfortably while driving during the day
 - b. My vision was clear enough to allow me to drive at night
 - c. Reduction in the feeling of tired eyes from using a computer or other digital device

A non-inferiority margin of 10% will be used.

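### As printed, section 14.7 puts 'Excellent' and 'Poor' in the same category for two of the three exploratory items and defines no second category

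*Combined protocol and SAP*

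**What the plan says.** Section 2.3 sets one exploratory hypothesis: after about a week of wear the test lens is non-inferior to control "with respect to at least one of the following subjective questionnaire items asked at the follow-up visit". Three items are listed: daytime driving, night driving and tired eyes from digital devices.

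Section 14.7 codes two of them under one subheading, "Ability to see comfortably while driving during the day or Reduction in the feeling of tired eyes from using a computer or other digital device". The single coding sentence makes the outcome "defined as category one if a subject's response is 'Excellent', 'Very Good', 'Fair', or 'Poor", and stops there.

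The night-driving item has its own paragraph. There the outcome is "category one if a subject's response is 'Strongly Agree' or 'Agree", and it is "category two if a subject's response is 'Not Applicable', 'Strongly Disagree', 'Disagree', or 'Neither Agree nor Disagree".

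All three items are then handled in the same way: "The outcome for each item will be analyzed separately using a generalized linear mixed model with a binary distribution and the logit as the link". Test and control are compared by "2-sided 95% confidence intervals (CIs) constructed for the odds ratio (test over control"), and the decision rule is "Non-inferiority will be concluded if a lower limit of a 95% CI is above 0.67".

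**The concern.** A binary logit model with an odds ratio of test over control needs two categories, one of them clearly the favourable one. The sentence for daytime driving and tired eyes supplies neither: it names one category, and that category spans both ends of the scale. The night-driving rule shows that the plan meant a favourable-versus-other split, so the sentence does not do what its neighbour does.

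At stake is whether two of the three exploratory comparisons can be interpreted. There is also a question of timing. The direction of the intended split is easy to guess, but the cut point is not. If it is left open, it could be settled after data are seen, in a trial where section 5.2 says investigators, site staff and sponsor personnel know which lens is which.

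**Working it through.** The plan gives no sample size or power for the exploratory items, so there is no stated figure to reproduce. The check sets the two coding rules side by side and then follows the printed rule through the model.

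**1. The two rules in section 14.7**

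- Night driving. Category one: 'Strongly Agree', 'Agree'. Category two: 'Neither Agree nor Disagree', 'Disagree', 'Strongly Disagree', 'Not Applicable'. Every listed answer is placed, and favourable answers stand alone.
- Daytime driving and tired eyes. Category one: 'Excellent', 'Very Good', 'Fair', 'Poor'. Category two: not defined. 'Good' and 'Not Applicable' are not mentioned.

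No other section available gives a different coding. The questionnaires in Appendix A are not shown, so the actual response scale is unknown. Two readings follow.

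**2. Reading A: the four listed responses are the whole scale**

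Every responder is in category one on both lenses, so the proportion is p = 1 for test and for control. The odds p/(1 − p) have a zero denominator and the odds ratio cannot be estimated.

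**3. Reading B: other responses, such as 'Good', form the complement**

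The distributions below are assumptions for illustration, in the order Excellent / Very Good / Good / Fair / Poor:

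- favourable lens: 40 / 35 / 15 / 7 / 3%
- unfavourable lens (mirror image): 3 / 7 / 15 / 35 / 40%

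Coding as printed, category one = Excellent + Very Good + Fair + Poor:

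- favourable: 40 + 35 + 7 + 3 = 85%
- unfavourable: 3 + 7 + 35 + 40 = 85%
- odds ratio, unfavourable over favourable = (0.85/0.15) / (0.85/0.15) = 1.00

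Coding with an assumed top-two split, category one = Excellent + Very Good:

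- favourable: 40 + 35 = 75%
- unfavourable: 3 + 7 = 10%
- odds ratio = (0.10/0.90) / (0.75/0.25) = 0.111 / 3 = 0.037

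The printed coding sees no difference between two lenses that a conventional split separates widely. For a single subject, 'Excellent' on control and 'Poor' on test are both category one and contribute no change.

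**4. Could such an item meet the 0.67 criterion under reading B?**

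Assume 165 completers (the target in section 4.3), 85% in category one on both lenses, and a simple marginal approximation with within-subject correlation r:

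- SE(log OR) = √[2(1 − r) / (n p (1 − p))]
- r = 0: √[2 / (165 × 0.85 × 0.15)] = √(2 / 21.04) = 0.308. Lower limit = exp(−1.96 × 0.308) = 0.55, which is below 0.67.
- To exceed 0.67: 1.96 × 0.308 × √(1 − r) < −ln 0.67 = 0.400, so 1 − r < (0.400/0.604)² = 0.44 and r > 0.56.

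A pass is therefore possible but not assured. It depends on a correlation and a response distribution that the documents do not give.

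**The case against.** The strongest reply is that this may be a gap in the converted text and not in the plan. The night-driving sentence closes category one after the favourable answers, then opens category two with 'Not Applicable'. The disputed sentence lacks three things: 'Good', the category-two clause and 'Not Applicable'. All three could sit at one point, between 'Very Good' and 'Fair', so a single lost line would explain every anomaly and could still leave a grammatical sentence. The converted text is visibly faulty elsewhere: in Table 6 the minor out-of-window entry seems to have lost a relational sign, and Table 8 prints the rotation limits without theirs. This is plausible and lowers confidence. It is not proven: the passage is continuous prose with no redaction mark, and nothing else available corrects it.

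Second, section 14.1 defers detail to a stand-alone SAP, which is not available here and may state the coding properly. That cannot be confirmed either way. An analyst would also have to define a second category before fitting the model, so the gap would probably surface in programming. True, but that is the moment at which an undocumented cut would be chosen.

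Third, the stakes are small. The items lie outside the sequential testing strategy of section 14.4, and no sample size rests on them. This stands, and it sets the severity.

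**Conclusion.** The point holds as a low-severity defect in the printed rule. On either reading of the scale, the coding for daytime driving and tired eyes cannot answer the non-inferiority question. It affects two of the three exploratory items and nothing else: primary and secondary hypotheses, sample size and type I error control are unchanged. The conclusion assumes that the sentence in the source document reads as it does here and that no separate SAP overrides it.

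Three stronger readings are tempting and are not supported.

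- A reader might infer that nearly every subject would fall in category one. That depends on how many answer 'Good' or 'Not Applicable', and neither the scale nor any response distribution is shown. Only under reading A is everyone in category one.
- A reader might infer that a mis-coded item would carry the exploratory claim, since one item of three suffices. Under reading A there is no estimate, so it cannot. Under reading B the coding can hide a real difference, but step 4 shows that a pass depends on unstated quantities.
- A reader might take it as established that the plan itself is wrong. The lost-line explanation has not been excluded.

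**What to change.** First compare the sentence in section 14.7 with the source document and with any stand-alone SAP. If a full two-category rule is there, no change to the plan is needed.

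If the sentence does read as printed, restate it before database lock:

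- Category one: 'Excellent' and 'Very Good', plus 'Good' if it is on the scale and the sponsor intends it as favourable.
- Category two: all remaining responses, including 'Fair' and 'Poor'.
- 'Not Applicable', if it is offered for these items: treat it consistently with night driving, where the plan puts it in category two. A different treatment would need a stated reason.

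The sponsor has to supply the position of 'Good', because the documents do not settle it. The cost is one sentence in section 14.7 and the SAP. Data collection, the model and the sample size stay as they are.

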14.8. Interim Analysis

Not applicable.

14.9. Procedure for Handling Missing Data and Drop-Outs

Missing or spurious values will not be imputed. The count of missing values will be included in the summary tables and listings.

Subject dropout is expected to be one of the main reasons of missing data in this clinical trial. Past clinical trials don't provide the evidence that subject dropout is systematic or not-at-random. To evaluate the impact of missing data, sensitivity analysis will be conducted using multiple imputation methods if the proportion of subject dropout is greater than the 15%. The SAS/STAT procedures PROC MI and PROC MIANALYZE will be utilized with a parametric regression method used to make at least 50 imputations.

14.10. Procedure for Reporting Deviations from Statistical Plan

The analysis will be conducted according to that specified in above sections. There are no known reasons for which it is planned to deviate from these analysis methods. If for any reason a change is made, the change will be documented in the study report along with a justification for the change.

15. DATA HANDLING AND RECORD KEEPING/ARCHIVING

15.1. Electronic Case Report Form/Data Collection

The data for this study will be captured on electronic case report forms (eCRFs) using the BioClinica EDC system. An authorized data originator will enter study data into the eCRFs using the EDC system. Data collected on equipment that is not captured in EDC will be formatted to the specification of the JJVC database manager and sent to JJVC for analysis.

No external data sources will be included in this study.

The clinical data will be recorded on dedicated eCRFs specifically designed to match the study procedures for each visit. Only specifically delegated staff can enter data on a CRF. Once completed, the eCRFs will be reviewed for accuracy and completeness and signed by the Investigator. The sponsor or sponsor's representatives will be authorized to gain access to the subject recordation for the purposes of monitoring and auditing the study.

Edit checks, electronic queries, and audit trails are built into the system to ensure accurate and complete data collection. Data will be transmitted from the clinical site to a secure central database as forms are completed or

Clinical Study Protocol
Johnson & Johnson Vision Care, Inc.

updated, ensuring information accuracy, security, and confidentiality. After the final database lock, the Investigator will be provided with Individual Patient Profiles (IPP) including the full audit trail on electronic media in PDF format for all of the study data. The IPP must be retained in the study files as a certified copy of the source data for the study.

The content and structure of the eCRFs are compliant with ISO14155:2020.¹

15.2. Subject Record

At a minimum, subject record should be available for the following:

- subject identification
- eligibility
- study identification
- study discussion
- provision of and date of informed consent
- visit dates
- results of safety and efficacy parameters as required by the protocol
- a record of all adverse events
- follow-up of adverse events
- medical history and concomitant medication
- test article receipt/dispensing/return records
- date of study completion
- reason for early discontinuation of test article or withdrawal from the study, if applicable

The subject record is the eCRF or an external record. The author of an entry in the subject record must be identifiable. The first point of entry is considered to be the source record.

Adverse event notes must be reviewed and initialed by the Investigator.

15.3. Trial Registration on ClinicalTrials.gov

This study will be registered on ClinicalTrials.gov by the Sponsor.

16. DATA MANAGEMENT

16.1. Access to Source Data/Document

The Investigator/Institution will permit trial-related monitoring, audits, IEC/IRB review and regulatory inspection(s) by providing direct access to source data/documents. Should the clinical site be contacted for an audit by an IEC/IRB or regulatory authority, JJVC must be contacted and notified in writing within 24 hours.

16.2. Confidentiality of Information

Information concerning the investigational product and patent application processes, scientific data or other pertinent information is confidential and remains the property of JJVC. The Investigator may use this information for the purposes of the study only. It is understood by the Investigator that JJVC will use information developed in this clinical study in connection with the development of the investigational product and therefore may disclose it as required to other clinical investigators and to regulatory agencies. In order to allow the use of the information derived from this clinical study, the Investigator understands that he/she has an obligation to provide complete test results and all data developed during this study to the Sponsor.

16.3. Data Quality Assurance

Steps will be taken to ensure the accuracy and reliability of data, including the selection of qualified investigators and appropriate clinical sites and review of protocol procedures with the Principal Investigator. The Principal

Clinical Study Protocol
Johnson & Johnson Vision Care, Inc.

Investigator, in turn, must ensure that all Sub-Investigators and clinical site personnel are familiar with the protocol and all study-specific procedures and have appropriate knowledge of the study article.

Training on case report form completion will be provided to clinical site personnel before the start of the study. The Sponsor will review case report forms for accuracy and completeness remotely during the conduct of the study, during monitoring visits, and after transmission to data management. Any data discrepancies will be resolved with the Investigator or designee, as appropriate.

Quality Assurance representatives from JJVC may visit clinical sites to review data produced during the study and to access compliance with applicable regulations pertaining to the conduct of clinical trials. The clinical sites will provide direct access to study-related source data/documents and reports for the purpose of monitoring and auditing by JJVC and for inspection by local and regulatory authorities.

16.4. Data Monitoring Committee (DMC)

Not applicable.

17. CLINICAL MONITORING

The study monitors will maintain close contact with the Principal Investigator and the Investigator's designated clinical site personnel. The monitor's responsibilities will include:

- Ensuring that the investigation is being conducted according to the protocol, any subsequent versions, and regulatory requirements are maintained.
- Ensuring the rights and wellbeing of subjects are protected.
- Ensuring adequate resources, including facilities, laboratories, equipment, and qualified clinical site personnel.
- Ensuring that protocol deviations are documented with corrective action plans, as applicable.
- Ensuring that the clinical site has sufficient test article and supplies.
- Clarifying questions regarding the study.
- Resolving study issues or problems that may arise.
- Reviewing of study records and source documentation verification in accordance with the monitoring plan.

18. ETHICAL AND REGULATORY ASPECTS

18.1. Study-Specific Design Considerations

Potential subjects will be fully informed of the risks and requirements of the study, and, during the study, subjects will be given any new information that may affect their decision to continue participation. Subjects will be told that their consent to participate in the study is voluntary and may be withdrawn at any time with no reason given and without penalty or loss of benefits to which they would otherwise be entitled. Subjects will only be enrolled if they are fully able to understand the risks, benefits, and potential adverse events of the study and provide their consent voluntarily.

18.2. Investigator Responsibility

The Principal Investigator is responsible for ensuring that the clinical study is performed in accordance with the signed agreement, the investigational plan, according to ISO 14155:2020,¹ and applicable regulatory requirements. GCP is an international ethical and scientific quality standard for designing, conducting, recording, and reporting studies that involve the participation of human subjects. Compliance with this standard provides public assurance that the rights, safety, and well-being of study subjects are protected, consistent with the principles of the Declaration of Helsinki 64th WMA General Assembly 2013² and that the clinical study data are credible. The Investigator must maintain clinical study files in accordance with applicable regulatory requirements.

Clinical Study Protocol
Johnson & Johnson Vision Care, Inc.

18.3. Independent Ethics Committee or Institutional Review Board (IEC/IRB)

Before the start of the study, the Investigator (or Sponsor when applicable) will provide the IEC/IRB with current and complete copies of the following documents (where applicable):

- Final protocol.
- Sponsor-approved informed consent form (and any other written materials to be provided to the subjects)
- Investigator's Brochure (or equivalent information).
- Sponsor-approved subject recruitment materials.
- Information on compensation for study-related injuries or payment to subjects for participation in the study.
- Investigator's curriculum vitae, clinical licenses, or equivalent information (unless not required, as documented by IEC/IRB).
- Information regarding funding, name of the Sponsor, institutional affiliations, other potential conflicts of interest, and incentives for subjects.
- Any other documents that the IEC/IRB requests to fulfill its obligation.

This study will be undertaken only after IEC/IRB has given full approval of the final protocol, the informed consent form, applicable recruiting materials, and subject compensation programs, and the Sponsor has received a copy of this approval. This approval letter must be dated and must clearly identify the documents being approved.

During the study, the Investigator (or Sponsor when applicable) will send the following documents to the IEC/IRB for their review and approval, where appropriate:

- Protocol revisions
- Revision(s) to informed consent form and any other written materials to be provided to subjects
- If applicable, new or revised subject recruitment materials approved by the Sponsor
- Revisions to compensation for study-related injuries or payment to subjects for participation in the study
- Investigator's Brochure revisions
- Summaries of the status of the study (at least annually or at intervals stipulated in guidelines of the IEC/IRB)
- Reports of adverse events that are serious, unanticipated, and associated with the test articles, according to the IRB's requirements
- New information that may adversely affect the safety of the subjects or the conduct of the study
- Major protocol deviations as required by the IEC/IRB
- Report of deaths of subjects under the Investigator's care
- Notification if a new Investigator is responsible for the study at the clinical site
- Any other requirements of the IEC/IRB

For protocol revisions that increase subject risk, the revisions and applicable informed consent form revisions must be submitted promptly to the IEC/IRB for review and approval before implementation of the change(s).

At least once a year, the IEC/IRB will review and reapprove this clinical study. This request should be documented in writing.

At the end of the study, the Investigator (or Sponsor where required) will notify the IEC/IRB about the study completion. Documentation of this notification must be retained at the clinical site and a copy provided to the CRO or Sponsor as applicable.

